6.1.2 Treatment Phase

6.1.2.1 Week 0 (Baseline/Pre-Intervention), Week 6 (Post-Intervention), Week 12 (Post-Intervention; waitlist control participants only)

The pre- and post-intervention visits will take place at the beginning and the end of the intervention period. Participants in both arms will meet remotely with a member of the research team via a HIPAA-compliant video conferencing platform (Zoom). The full battery of cognitive tasks (~35 minutes), functional assessments (~30 minutes), and mood symptom scales (~10 minutes) will be conducted at the baseline visit. Participants in the AKL-T01 intervention arm will be trained in procedures for gameplay during this visit. (Note that the week 6 assessment session will also serve as the baseline assessment for control participants who begin the intervention following the waitlist period.)

The pre- and post-intervention assessment visits will include the following study procedures:

- **Cognitive Tasks:**
- Digit Symbol Matching

- Multiple Object Tracking
- Digit Span Backwards
- Simple RT
- Choice RT
- Letter/Number Switch
- Gradual CPT
- Visual Paired Associates
- **Functional Assessments:**
- NeuroQOL
- WHODAS (36-item)
- Modified Fatigue Impact Scale
- **Mood Symptom Scales:**
- PHQ-9
- GADS-7

6.1.2.2 Weeks 2 & 4 (\pm 2 days; *all participants*) & Weeks 8 & 10 (\pm 2 days; *waitlist control participants only*)

The intermediate assessment visits at weeks 2 & 4 (and weeks 8 & 10 for waitlist control participants) will include a shorter battery of cognitive tasks (~25 minutes) and functional assessments (~10 minutes) measuring the primary and secondary endpoints, as well as the PHQ-9 (~5 minutes) for monitoring of mood symptoms.

The intermediate assessment visits will include the following study procedures:

- **Cognitive Tasks:**
- Digit Symbol Matching
- Multiple Object Tracking
- Digit Span Backwards
- Simple RT
- Choice RT
- Letter/Number Switch
- Gradual CPT
- **Functional Assessments:**
- NeuroQOL
- WHODAS (12-item)
- **Mood Symptom Scales:**
- PHQ-9

6.1.3 Follow-up Phase

Longitudinal follow-up assessment visits will take place 4 weeks after the end of the intervention period. For participants in the AKL-T01 intervention arm this visit will take place at week 10. For participants in the control arm who do begin the intervention at the end of the waitlist period, this visit will take place at week 16. This visit will include the full battery of cognitive tasks, functional assessments, and mood symptom scales collected at the pre- and post-intervention visits.

7. Study Intervention

7.1 Study Intervention/Device Description

The AKL-T01 intervention and the study assessments will be administered on an Apple iPad. The intervention video game is an iPad application that will be pre-installed on the iPads provided to participants. The iPad will also include shortcuts to the cognitive tasks and the RedCap database through which they will complete the self-report scales. All other applications and web pages will be locked on the intervention iPads. Participants in both the intervention arm and the waitlist control arm will be provided with iPads to ensure consistency in the data collection device.

The iPads will be shipped to participants' homes with a self-addressed return envelope for the iPad to be mailed back to the research team at the conclusion of participation in the study.

7.2 Availability

An Apple iPad will be provided to the participants for the duration of their participation by Akili Interactive.

7.3 Acquisition and Accountability

iPad Device Logs – The investigator, or a responsible party designated by the investigator, will maintain a careful record of the inventory and disposition of all iPads received from Akili Interactive in the study's Device Log.

7.4 Formulation, Appearance, Packaging, and Labeling

The devices provided to the participants will be Apple iPads. Participants will only be able to access the AKL-T01 video game interface (intervention arm only), the cognitive task battery, and the RedCap database for assessment administration. Participants will review instructions for using the iPads with a member of the research team during their first weekly check-in visit.

7.5 Product Storage and Stability

Not applicable.

7.6 Preparation

Not applicable.

7.7 Dosing and Administration

Participants in the AKL-T01 intervention arm are required to play the game for 25 minutes per day for at least five days (but up to 7 days) per week. The game will automatically "lock" after 25 minutes to prevent participants for playing longer than specified.

7.7.1 Dosing Delays/Dose Modifications

Not applicable.

7.8 General Concomitant Medication and Supportive Care Guidelines

Not applicable.

7.9 Duration of Therapy and Criteria for Removal from Study

In the absence of intervention delays due to adverse event(s), intervention may continue until one of the following criteria applies:

- Intercurrent illness that prevents further administration of the intervention,
- Unacceptable adverse event(s),
- Subject decides to withdraw from the study, or
- General or specific changes in the subject's condition render the subject unacceptable for further intervention in the judgment of the investigator.
- The investigators of this study may stop the study or remove participants from the study at any time should they judge that it is in the participants' best interest to do so or if they do not comply with the study plan.

For device/interventional studies -

Study Termination Guidelines: A subject's follow-up in the study will end after one of the following applies:

- Subject's voluntary withdrawal
- Subject lost to follow-up
- Completion of all scheduled study follow-up appointments

7.10 Duration of Follow Up

Subjects removed from study for unacceptable adverse events will be followed until resolution or stabilization of the adverse event.

7.11 Measures to Minimize Bias: Randomization and Blinding

A WCM data manager not involved in any other aspects of the study will use a computer-generated randomization table to determine whether the patient will be assigned to the AKL-T01 intervention arm or the waitlist control arm.

Participants will be aware of their assignment to study arm because it is not possible to blind them. The researchers conducting the study assessments will be blind to assignments. The care managers will not be blinded because it is not possible to blind them and it is necessary for them to know of a participant's assignment to assist in troubleshooting.

Participants and care managers will be instructed not to reveal the group assignment to the member of the research team conducting assessments. Following the completion of recruitment, data analysts will be provided with the data for the arms simply labelled as "Group A" and "Group B" to avoid bias. These generic labels will be unmasked only after completion of all the planned statistical analyses described below. Participants in the waitlist control arm who begin the intervention at the end of the waitlist period will have different

assessors for the initial 6-week control procedures and the subsequent 6-week intervention period so as to maintain the blind.

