1.2.6 Exploratory Endpoints

- 1) Long-term change in cognition and daily functioning 4 weeks following the end of the intervention will be assessed by calculating change scores from baseline to week 10 and from week 6 to week 10 in our primary and secondary measures of cognitive and daily function.
- 2) To explore improvement in far transfer to an untrained cognitive domain, we will calculate mean change in score on the Visual Paired Associates task from pre-intervention (baseline) to post-intervention (week 6).
- 3) The exploratory endpoint for our measure of fatigue is mean change in Modified Fatigue Impact Scale score from pre-intervention (baseline) to post-intervention (week 6).
- 4) The exploratory endpoints for our measure of mood symptoms is mean change in PHQ-9 and GADS-7 scores from pre-intervention (baseline) to post-intervention (week 6).

2. Background

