For participants without access to technology that would allow them to consent electronically, the participant and researcher will review the consent form over the phone. A copy of the consent form will be mailed or emailed to the participant in advance so that it can be viewed by the participant during the phone call. They will return the signed consent form in a stamped, self-addressed envelope provided by the researcher. These participants will then be mailed a copy of their signed consent form for their records.

To screen prospective participants, we will conduct an initial screening via a secure HIPAA-compliant videoconferencing platform (Zoom). Participants will be queried for inclusion and exclusion criteria. Participants will be administered via Zoom the Oral Trail Making Test, Stroop Test, and the Frontal Systems Behavior Rating Scale (FrSBe). Participants will be eligible for enrollment if they score <1 standard deviation below their age-normed peers on at least one of these three screening tests.

Participants will be randomized into the intervention arm or a waitlist control arm, with an option for the control participants to receive the AKL-T01 intervention at the conclusion of the initial 6-week waitlist period.

All participants (intervention & waitlist control arm): Full assessment visits will take place pre-intervention (baseline) and post-intervention (week 6). During the 6-week intervention period, shorter intermediate assessment visits will take place at weeks 2 and 4. Participants in the waitlist control arm will continue any ongoing self- or provider-based cognitive intervention (or no intervention) during the initial 6-week waitlist period.

Participants in the intervention arm & participants in the control arm who decline the intervention: A full assessment session at will take place at week 10 (4 weeks post-intervention) for longitudinal follow-up.

Participants in the control arm who begin the intervention at the conclusion of the waitlist period: The week 6 assessment visit will also serve as the baseline for the beginning of the intervention. Intermediate assessment visits will take place at weeks 8 and 10, a full post-intervention assessment visit will take place at week 12, and a follow-up assessment visit will take place at week 16 (4 weeks post-intervention).

See Section 6.1 for the complete Schedule of Assessments.

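### Section 7.11 masks analysts until all planned analyses are finished but does not limit which visits they receive, and any data after week 6 can show which group is the waitlist arm

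*Combined protocol and SAP*

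**What the plan says.** Section 7.11 describes the analyst mask in two steps. "Following the completion of recruitment, data analysts will be provided with the data for the arms simply labelled as" Group A and Group B, and then: "These generic labels will be unmasked only after completion of all the planned statistical analyses described below". It does not name the visits or variables in that release, and it sets no cut at week 6.

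Section 3.1 gives different schedules after week 6. For waitlist participants who start AKL-T01: "Intermediate assessment visits will take place at weeks 8 and 10, a full post-intervention assessment visit will take place at week 12", with a final follow-up at week 16. For the AKL-T01 arm and for waitlist participants who decline: "A full assessment session at will take place at week 10 (4 weeks post-intervention) for longitudinal follow-up". Section 6.1.2.2 adds that the content differs too: "The intermediate assessment visits at weeks 2 & 4 (and weeks 8 & 10 for waitlist control participants) will include a shorter battery".

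Section 1.2.6 defines the follow-up endpoint as "calculating change scores from baseline to week 10 and from week 6 to week 10 in our primary and secondary measures" of cognition and daily function. Section 10.1, which comes after 7.11, lists improvement at this follow-up among the exploratory outcomes.

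**The concern.** The mask is a label on a whole group. If a single record shows that Group B contains a waitlist participant, both labels are decoded. The crossover schedule produces such records, and a planned outcome uses data from the same period.

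Analyst masking carries some weight in this trial. Participants and care managers know the assignment. The plan also leaves choices to the analyst:

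- Section 10 specifies a linear mixed model with a group-by-time term, while Sections 12.1 and 12.4.1 specify ANOVA on change scores.
- Section 10 allows adjustment for baseline confounders that are identified later.
- Section 10.1 lets improvement on the secondary cognitive tasks mean accuracy, response time or both.
- Neither Section 10 nor Section 12 names a method for missing data.

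These are the decisions that masking is meant to protect. Section 7.11 does recognise that crossover threatens blinding, since it gives crossover participants different assessors for the two periods. It gives the analysts no matching protection.

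**Working it through.** **1. Confirm the schedule from the plan's own figures.** The compensation table in Section 4.6 states totals of $225, $225 and $325. Adding the payments over each path's visits gives:

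- AKL-T01 arm, weeks 0, 2, 4, 6, 10: 50 + 25 + 25 + 50 + 75 = $225.
- Waitlist, declines AKL-T01, weeks 0, 2, 4, 6, 10: 50 + 25 + 25 + 50 + 75 = $225.
- Waitlist, crosses over, weeks 0, 2, 4, 6, 8, 10, 12, 16: 50 + 25 + 25 + 50 + 25 + 25 + 50 + 75 = $325.

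All three totals are reproduced, so the payment table and Section 3.1 describe the same schedule. The legend of Table 1 in Section 6.1, as it reads in the available text, does not fit this schedule. That may be a fault of text extraction, and nothing here relies on it.

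**2. Find the visits that reveal the arm.** Weeks {0, 2, 4, 6, 8, 10, 12, 16} minus {0, 2, 4, 6, 10} leaves {8, 12, 16}. These occur only in waitlist crossovers. Up to week 6 both arms have visits at 0, 2, 4 and 6, so the scheduled visits give no clue.

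**3. Check week 10, the visit that the follow-up endpoint needs.** Crossovers have the intermediate battery: the 12-item WHODAS and no Visual Paired Associates (Section 6.1.2.2). The AKL-T01 arm and the decliners have the full battery, with the 36-item WHODAS (Sections 3.1, 6.1.2.1 and 6.1.3). WHODAS is a secondary measure and so falls within the Section 1.2.6 endpoint. The week-10 data therefore reveal the arm even if weeks 8, 12 and 16 are withheld.

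**4. Chance that at least one such record exists.** The waitlist arm has 50 participants (Section 12.2). Uptake p is not stated, so the values below are assumptions. P(at least one) = 1 − (1 − p)^50:

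| Assumed uptake | Expected crossovers | P(at least one) |
|---|---|---|
| 1% | 0.5 | 1 − 0.99^50 = 39.5% |
| 2% | 1.0 | 1 − 0.98^50 = 63.6% |
| 5% | 2.5 | 1 − 0.95^50 = 92.3% |
| 10% | 5.0 | 1 − 0.90^50 = 99.5% |
| 25% | 12.5 | about 100% |

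**5. Timing.** Section 7.11 releases data after recruitment, which is expected to take 12 months. Assuming steady accrual over 52 weeks, about (52 − 8)/52 = 85% of controls, or 42 of 50, would be past week 8 when recruitment closes. With 40 as a round lower figure, the chance is 1 − 0.95^40 = 87.1% at 5% uptake and 1 − 0.90^40 = 98.5% at 10%. Waiting for the last participant is not needed for revealing records to be present.

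**The case against.** The strongest reply is that Section 7.11 does not say the full dataset is handed over. It mentions the data for the arms and is silent on visits, on the number of exports and on dashboard data. It also refers to analyses described below it, and the tests given after it compare week 0 with week 6 (Sections 10, 12.1 and 12.4.1). On that reading the masked work can be done on a week 0 to 6 extract, and a careful data manager would produce one.

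Much of this stands. The loss of masking is conditional on the release, and a week-6 cut is a fair reading. It does not remove the gap, because nothing requires the cut, and Section 10.1 also comes after 7.11 and lists the follow-up outcome, although it gives no model for it. Taken literally, the plan keeps analysts masked while they work on week-10 data that show the arm.

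Two stronger inferences are not supported. A reader might conclude that the week-6 result is biased. The percentages above give only the chance that the arms could be recognised if later data are released. They say nothing about the treatment estimate, and assessor blinding is unaffected. A reader might also conclude that gameplay data would unmask the analysts. Sections 7.12 and 11.1 show that such data are collected, but no section says analysts receive them, and no analysis in Section 10 or 12 uses them.

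It is also fair to object that a week-6 cut alone is not enough. Section 8.1 collects the post-intervention battery when AKL-T01 is discontinued. During weeks 0 to 6 only the intervention arm can discontinue it, so an off-schedule full battery could reveal the arm inside the extract. The fix has to cover this.

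**Conclusion.** The point holds as a gap in a stated bias control. Section 7.11 promises masking through all planned analyses, but the schedule after week 6 cannot deliver it for the follow-up outcome once any control has crossed over. It protects the week-6 primary and secondary analyses only if later data are held back, which the plan does not require.

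The conclusion rests on two assumptions. The first is that some post-week-6 data reach the analysts before the week-6 analyses are complete, which the documents neither state nor prevent. The second is that at least one of the 50 controls crosses over: 92.3% likely at 5% uptake, 99.5% at 10%, and only 39.5% at 1%. The documents do not support a claim that masking will certainly be lost. The change is still worth making, because the primary model is unsettled between Sections 10 and 12 and the remedy is cheap.

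**What to change.** Amend Section 7.11 to a two-step release.

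- **Step 1.** Give analysts only the week 0, 2, 4 and 6 outcome data under Group A and Group B labels. Include no crossover flag, no visit dates after week 6 and no gameplay data, should these be in the export. Map early-discontinuation assessments under Section 8.1 to nominal visits without a flag, by a rule written beforehand, so that measures belonging only to the full battery do not appear at week 2 or 4. Complete and archive all week-6 analyses.
- **Step 2.** Release the week 8 to 16 data, and describe the analyses of those visits as unmasked.

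The cost is protocol wording and one extra export by the data manager. Visits, participants and sample size do not change. The downside is that the follow-up analyses are openly reported as unmasked. The two-step release does not by itself cover the interim analyses that Section 12.5 allows on request. These need their own statement of who sees which data.

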7.12 Study Intervention/Follow-up Compliance

Adherence to video game play for the participants in the AKL-T01 intervention arm will be monitored by a member of the research team using the intervention dashboard, which provides the researchers with information about duration and frequency of gameplay, progression through game levels, etc. Participants who are not playing for the required duration of 25 minutes a day for at least 5 days a week will work with their care manager during a weekly check-in visit to make a plan for game play (e.g., playing at a specific time each day, setting reminders to play).

Participants will be considered lost to follow up and no longer participating in the study when they do not respond to attempts at communication with the researcher for two weeks and miss an assessment visit during that window.

8. Study Intervention Discontinuation and Participant Discontinuation/Withdrawal

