8.2 Participant Discontinuation/Withdrawal from the Study

Participants are free to withdraw from participation in the study at any time upon request. An investigator may discontinue or withdraw a participant from the study for the following reasons:

- Significant study intervention non-compliance
- If any clinical adverse event (AE), laboratory abnormality, or other medical condition or situation occurs such that continued participation in the study would not be in the best interest of the participant.
- Participant lost to follow-up after several attempts to contact subject to schedule study visit.

The reason for participant discontinuation or withdrawal from the study will be recorded in the case report form (CRF). Subjects who sign the informed consent form and are randomized but do not receive the study intervention may be replaced. Subjects who sign the informed consent form, and are randomized and receive the study intervention, and subsequently withdraw, or are withdrawn or discontinued from the study, will not be replaced.

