8.3 Lost to Follow Up

A participant will be considered lost to follow-up if they do not complete a scheduled visit within two weeks of the assessment window and is unable to be contacted by the study site staff.

The following actions must be taken if a participant does not complete a required study visit:

- The site will attempt to contact the participant and reschedule the missed visit for two weeks and counsel the participant on the importance of maintaining the assigned visit schedule and ascertain if the participant wishes to and/or should continue in the study.
- Before a participant is deemed lost to follow-up, the investigator or designee will make every effort to regain contact with the participant (where possible, 3 telephone calls and, if necessary, a certified letter to the participant's last known mailing address or local equivalent methods). These contact attempts should be documented in the participant's medical record or study file.
- Should the participant continue to be unreachable, he or she will be considered to have withdrawn from the study with a primary reason of lost to follow-up.

9. Correlative/Special Studies

Not applicable.

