12.4 Analysis of Endpoints

12.4.1 Analysis of Primary Endpoints

Our primary cognitive measure will be change in performance on a Digit Symbol Matching Task from baseline (pre-intervention) to week 6 (post-intervention) in all participants randomized to the intervention or control arm. Our primary daily functioning measure will be change in score on the NeuroQOL Cognitive Function scale from baseline (pre-intervention) to week 6 (post-intervention) in all participants randomized to the intervention or control arm. We will use analysis of variance (ANOVA) to test for differences in Digit Symbol Matching and NeuroQOL change scores across the two arms.

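### Sections 7.12 and 8.3 give different loss-to-follow-up rules, and both can close an unreachable participant before the week-6 primary assessment with no further attempt at it

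*Combined protocol and SAP*

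**What the plan says.** Section 7.12 opens its rule with "Participants will be considered lost to follow up and no longer participating in the study when they do not respond to attempts at communication". The full condition is that they "do not respond to attempts at communication with the researcher for two weeks and miss an assessment visit during that window". No number or type of contact attempt is given there.

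Section 8.3 applies its own rule to participants who "do not complete a scheduled visit within two weeks of the assessment window and is unable to be contacted" by site staff. It allows two weeks of attempts to reschedule. Before the label is applied it also calls for every effort to regain contact: "where possible, 3 telephone calls and, if necessary, a certified letter". If these fail, "he or she will be considered to have withdrawn from the study with a primary reason of lost to follow-up". Section 8.2 lists a third, looser version among the reasons for withdrawal: "Participant lost to follow-up after several attempts to contact subject to schedule study visit".

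Section 3.1 places intermediate assessments at weeks 2 and 4 and the post-intervention assessment at week 6. Section 12.4.1 defines the primary measure as change from baseline to week 6 "in all participants randomized to the intervention or control arm", and Section 12.1 specifies intent-to-treat.

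**The concern.** Two rules for the same status can classify the same participant differently, depending on which section a coordinator follows. The larger issue is common to both rules. Each can be triggered by a week-2 or week-4 assessment that the primary endpoint does not need, and each then ends participation. Neither section says that the week-6 assessment is still attempted.

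For someone who goes silent for a while and might have answered again by week 6, the protocol gives up the primary outcome by rule. Under the ANOVA in Section 12.4.1, a participant without a week-6 value has no change score. I found no method for missing outcomes in the statistical section. Section 8.1 already keeps people who stop the intervention in follow-up, but the loss-to-follow-up rules do not extend that principle to people who are temporarily out of contact.

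**Working it through.** **Inputs.** Weeks 2 and 4 fall on nominal days 14 and 28, with a window of plus or minus 2 days (Section 6.1.2.2). No window is given for week 6, so I take day 42. I count a visit as missed when its window closes: M = 14 + 2 = day 16 for week 2, and M = 28 + 2 = day 30 for week 4.

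**Section 7.12 read alone.** If silence begins on day S, closure falls on day S + 14, provided the missed visit lies within those 14 days. The earliest case is S = M - 14, which gives closure on day M. The latest is S = M, which gives closure on day M + 14.

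**Section 8.3.** Closure is not before window close plus 14 days, which is M + 14.

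| Missed assessment | 7.12, earliest | 7.12, latest | 8.3, earliest | Week 6 |
|---|---|---|---|---|
| Week 2 | day 16 | 16 + 14 = day 30 | 16 + 14 = day 30 | day 42 |
| Week 4 | day 30 | 30 + 14 = day 44 | 30 + 14 = day 44 | day 42 |

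- Week 2 missed: both rules can close the participant before day 42.
- Week 4 missed: 7.12 closes before day 42 whenever S + 14 < 42, that is, when silence began before day 28. Under 8.3 closure falls on day 44 at the earliest, after week 6 is due.
- Example: silence from day 20 with week 4 missed. 7.12 gives 20 + 14 = day 34. 8.3 gives day 44 at the earliest, ten days later. The largest gap between the rules is 14 days (day 30 against day 44).

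**How much the missed-visit condition filters.** Assessments up to week 6 are 14 days apart, so nearly any two-week silence in that period covers one. This does not hold later: the AKL-T01 arm and controls who decline the intervention have no assessment between weeks 6 and 10.

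**The plan's own figure.** This point disputes none. Section 12.2 states power above 88% (95% CI 80.0-93.6%) from 100 simulated data sets. The exact binomial interval for 88/100 is 80.0-93.6%, which agrees. The power itself cannot be reproduced, because the within-person correlation is not given.

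**Scale of lost week-6 data (assumed, not attributable to the rule).** Take a random-intercept model over weeks 0, 2, 4 and 6. The sum of squared deviations of time is 9 + 1 + 1 + 9 = 20, so the six-week change has SD = sqrt((36/20)(1 - ICC)) = sqrt(1.8(1 - ICC)). Setting ICC = 0.774 makes 50 per arm give 88% at d = 0.4, two-sided alpha 0.05. If lost participants contributed nothing, power would be 84.5% at 10% loss (45 per arm) and 80.1% at 20% (40 per arm). The standard error would rise by sqrt(50/45) = 1.054 and sqrt(50/40) = 1.118. These describe total loss from any cause. The mixed model in Section 10 would keep earlier visits and soften them.

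**The case against.** The best defence is that 7.12 is a short summary and 8.3 is the procedure. The requirement in 8.3 to make every effort before anyone is deemed lost is worded generally, so it can be read as governing the label in 7.12 too. Both sections need a missed visit and an unreachable participant, both use two weeks, and both end participation. On that reading the earlier closures under 7.12 arise only if 8.3 is ignored. This stands in part: the conflict is confined to the start of the clock and the contact effort. It does not remove the week-2 problem, which 8.3 has on its own at about day 30.

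A reader might make four stronger inferences that the documents do not support:

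- **One missed intermediate visit ends participation.** It does not. Someone who misses week 2 or 4 but stays in contact is not closed under either rule. Weekly check-ins run in both arms (Section 2.4.3), so two weeks of silence also spans about two failed check-ins.
- **7.12 is the sole cause, and deferring to 8.3 as it stands would cure it.** The week-2 arithmetic shows otherwise.
- **Loss will be uneven between arms and bias the result.** Section 3.2 mentions only a potential for dropout in controls, and at once gives mitigation through check-ins and compensation. Any bias figure needs assumed loss rates, an assumed difference in outcome between lost and retained people, and the fraction of loss due to the rule. None of these is in the documents.
- **The rules contradict intent-to-treat.** Declaring unreachable people lost is compatible with Section 12.1. The point is that outcome data which might be obtained are not sought.

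**Conclusion.** The point holds as an inconsistency to reconcile and a missed opportunity to protect the primary endpoint. Either rule can close an unreachable week-2 non-responder before week 6. For a week-4 non-responder, 7.12 read alone can do so and 8.3 cannot before about day 44. Closure before week 6 is possible, not automatic: if silence starts around the week-4 visit, 7.12 gives about day 40 to 44, close to week 6 itself. These dates assume week 6 is day 42.

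The number of people who would have returned for week 6, and the size or direction of any bias, cannot be derived from the documents. No sample-size or power figure is shown to be wrong. I class this as a cheap improvement.

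**What to change.** 1. Delete the loss-to-follow-up sentence from Section 7.12 and keep a single definition in 8.3, with the entry in 8.2 referring to it.
2. State that a missed week-2 or week-4 assessment, even with no contact, is a missed visit and does not end participation.
3. Attempt the week-6 assessment, identically in both arms, for every randomized participant who has not withdrawn consent.
4. Assign lost-to-follow-up status for the primary objective only after the week-6 visit and its two-week rescheduling period have passed and the 8.3 contact attempts have failed. Because 8.3 counts from a visit window, state one for week 6.

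The cost is a short protocol amendment and some extra contact attempts by existing staff, using remote visits that are already planned. The downside is that some of this effort goes to people who may not return.
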